1.4 Risk-Benefit Assessment

1.4.1 Benefits

In Study REN001-101, an open label Phase 1b study in subjects with mtDNA PMM, oral REN001 dosed at 100mg per day was safe and well tolerated for 12 weeks (Part A) and up to an additional 24 weeks in the subjects who continued into an extension part of the study (Part B). Following 12 weeks of dosing, most subjects experienced improvement in the outcome measures of distance walked in the 12MWT and symptoms of fatigue and pain evaluated with Patient Reported Outcome (PRO) measures. The study was terminated early in 2020 due to the operational obstacles created by the Corona Virus Disease 2019 (COVID-19) pandemic. Subjects who were ongoing in the study when Study REN001-101 was terminated will be given the opportunity for further treatment with REN001 in this study.

The STRIDE study is an ongoing double-blind, placebo-controlled, Phase 2b study to evaluate the efficacy and safety of 24 weeks treatment with REN001, dosed at 100mg per day, in mtDNA PMM subjects. This long-term safety study will offer the opportunity for extended active treatment for those subjects randomized to REN001 in STRIDE, and active treatment for subjects who were randomized to placebo. Neither subjects nor sites will be aware of the allocated treatment in STRIDE when rolling directly into this study, and the Sponsor will remain blinded to this information until the STRIDE database is locked and treatment allocation unblinded.

Patients with nDNA mutations will not have previously participated in studies in the REN001 program (due to eligibility criteria designed to maintain a homogenous population). However, the potential for REN001 to provide benefit for PMM patients is based on the myopathic phenotype, rather than specific genetic cause. Therefore, after gaining experience in the

mtDNA-PMM population, this protocol was amended (Version 2.0) to widen enrollment to include adult PMM patients with nDNA mutations. This will provide long-term safety data on the total PMM patient population and provide evidence of potential efficacy in the nDNA-PMM population.

This amendment increases the duration of the study from 24 months to 48 months. The duration of the study has been increased to continue the collection of long-term safety and also to enable access to REN001 therapy to those subjects who may be benefiting from REN001 treatment.

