 - the re-introduction of mavodelpar for subjects who had a break in mavodelpar treatment in studies REN001-101 or REN001-201; and
 - the introduction of mavodelpar for mavodelpar-naïve nDNA subjects.
- from the start of REN001-201. These presentations will focus on reporting Groups 1, 2, 3 and 4a and include data collected in both REN001-201 and REN001-202, except Group 4a, where only REN001-201 data will be included. This will continue to acknowledge the randomization to treatment groups at the start of the REN001-201. It will provide an insight on the influence of a 6-month delay in beginning mavodelpar on subject safety and efficacy outcomes. Importantly, this will summarize the data for all subjects randomized and dosed in REN001-201.
- from the start of REN001 treatment. These presentations will focus on reporting Groups 1, 2, 3 and 4 and include data collected in both REN001-201 and REN001-202 depending on when mavodelpar is initiated. This provides an overall summary of emergent data following the initiation of mavodelpar treatment to mtDNA-PMM

subjects. This is particularly important with respect to safety data (e.g., overall incidence of AEs with mavodelpar treatment).

For further details on the reporting groups refer to [Section 8.2](#).

The purpose of this SAP is to ensure that the data listings, summary tables and figures which will be produced, and the statistical methodologies that will be used, are comprehensive and appropriate for the assessment of study objectives specified in the study protocol. Changes from the analyses specified in the protocol will be identified in the SAP and any amendments to the SAP will be made prior to database lock. The SAP will be the point of reference for the analyses performed for the CSR. Any additional analyses not described in the final SAP or deviations from the final SAP will be documented in the CSR.

The SAP has been developed based on REN001-202 Protocol Version 3.0 and the latest CRF available (Version 6.0, Date 24 April 2023) and REN001-201 Protocol Version 4.0. The subsequent country specific protocol amendments for REN001-202 (see [Appendix 1](#)) do not impact the SAP.

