subjects represent. These 5 reporting groups are referenced in square brackets alongside the descriptions below. The summaries are:

- From the start of REN001-202 Summaries will be presented by mutation group (REN001 100 mg mtDNA-PMM [Groups 1 to 4] and REN001 100 mg nDNA-PMM [Group 5]). The mtDNA-PMM group will also be split by:
 - Placebo > REN001 100 mg [Group 1] – subjects who received placebo in REN001-201 and enrolled at REN001-201 W24, FU or after exit.
 - REN001 100 mg > REN001 100 mg [Group 2] – subjects who received mavodelpar in REN001-201 and enrolled at REN001-201 W24 visit.
 - REN001 100 mg >FU> REN001 100 mg [Group 3] – subjects who received mavodelpar in REN001-201 and enrolled at REN001-201 FU visit.
 - REN001 100 mg >Exit> REN001 100 mg [Groups 4a and 4b] – subjects who received mavodelpar in REN001-201 and enrolled after exiting REN001-201 or subjects who took part in REN001-101 study.

Summaries will extend out to Month 48, where applicable.

- From the start of REN001-201 which will be split by REN001-201 treatment group (REN001 100 mg [Groups 2, 3 and 4a] and placebo [Group 1]). Subjects who enrol in REN001-202 at REN001-201 Exit will only have their REN001-201 data included in these summaries. Baseline summary tables (disposition, demography, baseline characteristics, medical history and prior medications) will also include an overall summary.

Summaries will extend out to Month 54, where applicable, for all subjects who complete both studies.

- From the start of REN001 treatment [Groups 1, 2, 3 and 4]. Subjects who enrol in REN001-202 at REN001-201 Exit and receive mavodelpar in REN001-201 [Group 4a] will be counted as 2 separate subjects. Summaries will be presented over all subjects (REN001 100 mg).

Summaries will extend out to Month 54, where applicable, for subjects who receive mavodelpar in REN001-201 and enrol in REN001-202 at REN001-201 W24 or FU; for all other subjects summaries will extend to Month 48.

In addition, for summaries from the start of REN001 there is only Week 2 (Month 0.5), Week 18 (Month 4.5), Month 1 (Month 7) and Month 3 (Month 9) for subjects who receive mavodelpar in REN001-201 and therefore this visit will not be included in the by visit summaries. Refer to [Section 3.8](#) for diagram of visit assignment.

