12.1. ADVERSE EVENTS

AEs will be coded using MedDRA version 23.1.

AEs will be considered treatment-emergent (TE) unless there is a clear indication that the event occurred prior to the first administration of study drug. AEs with missing start dates will be taken as TE unless the end date occurs before Day 1. If there is a partial start date, then the AE will be taken as TE unless suggested otherwise by the partial information provided and the end date.

Any AEs reported prior to dosing in either REN001-201 or REN001-202 (for subjects enrolling at REN001-201 Exit, from REN001-101 or nDNA-PMM subjects) will be reported as pre-treatment AEs in the databases and will therefore not be reported as TE (checks will be made of the AE start date against the start of dosing). Subjects who receive placebo in REN001-201 will have their TE events reported in REN001-201 assigned to placebo. Any events that are ongoing at the start of REN001-202 will only be assigned to mavodelpar if they worsen in severity on or after the start of dosing in REN001-202.

Note, any ongoing AEs at the end of REN001-201 for subjects enrolling at REN001-201 W24 or REN001-201 FU will be recorded on the pre-treatment AE eCRF page for REN001-202; if the event resolves during REN001-202 the record will be updated. These events will be considered TE to the REN001-201 treatment.

If an adverse event has a missing start date where the stop date is after the dosing date, or missing, the date will be imputed as the dosing start date and for a missing start date where the stop date is before the start date of dosing, the date will be imputed as the day of informed consent and classified as a pre-treatment AE; for a missing stop date the TEAE will be considered as ongoing at the last visit date. If a partial date is recorded, the following convention will be used to assign the AE based on the database that the AE was recorded in:

- If a start date is missing the day information and month/year is the same as the dosing start date then use the dose start date, else '01' will be used for the day; if a start date is missing the day/month and the year is the same as the dosing start date then use the dose start date, else January will be used for the start month.

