12.5. ECG

Observed and change from baseline values will be summarized by visit using descriptive statistics.

A shift table from baseline to visit, for overall ECG interpretation (normal, abnormal not clinically significant, abnormal clinically significant and missing) will be summarised with marginal totals, using counts and percentages.

A shift table from baseline to the maximum post baseline QTcF value will be summarized according to the categories specified in the table below. The maximum will be taken from all scheduled and unscheduled on-treatment values.

Parameter	Criteria
QTcF	
< 450 msec
 
≥ 450 msec and < 480 msec*
 
≥ 480 msec and < 500 msec*
 
≥ 500 msec*

QTcF increase from baseline	
< 30 msec
 
≥ 30 msec and < 60 msec*
 
≥ 60 msec*

* Values of PCI.

Observed and change from baseline values will be listed. The listing will identify QTcF values of PCI (identified in the above table).

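### In the from-start-of-REN001-201 presentation, placebo PCI and maximum-QTcF counts include values first seen on open-label mavodelpar, and no column is named for Group 1's REN001-202 events in the overall AE table

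*SAP*

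**What the plan says.** SAP section 2 says the from-start-of-REN001-201 presentation will "include data collected in both REN001-201 and REN001-202, except Group 4a, where only REN001-201 data will be included". Section 8.2 gives it two columns, "split by REN001-201 treatment group (REN001 100 mg [Groups 2, 3 and 4a] and placebo [Group 1", and sets the horizon: "Summaries will extend out to Month 54, where applicable, for all subjects who complete both studies". It adds that "Subjects who enrol in REN001-202 at REN001-201 Exit will only have their REN001-201 data included in these summaries". Section 2 states the purpose: "It will provide an insight on the influence of a 6-month delay in beginning mavodelpar on subject safety and efficacy outcomes".

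Section 12 runs every safety evaluation on each safety set by default, so this presentation carries all the safety tables. Three rules matter for it:

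- **On-treatment (8.2).** A value counts as on-treatment through one day after the last dose. Interruptions are ignored, explicitly including the gap for subjects who enrol at the REN001-201 follow-up visit.
- **Laboratory PCI (12.2).** A subject counts if at least one on-treatment post-baseline value meets the criterion.
- **QTcF (12.5).** The shift is to the maximum post-baseline value: "The maximum will be taken from all scheduled and unscheduled on-treatment values".

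Adverse events have their own rules in 12.1: "Subjects who receive placebo in REN001-201 will have their TE events reported in REN001-201 assigned to placebo". Events ongoing at the start of REN001-202 pass to mavodelpar only on worsening. The summaries appear overall and by onset period, with boundaries at Days 28, 168 and 336. Section 7.2 says the safety summaries in this presentation follow the treatment actually received.

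**The concern.** Group 1 subjects who enter REN001-202 at Week 24 or at follow-up take mavodelpar from their first REN001-202 dose. In this presentation they stay in a column headed placebo, and no column or period is defined for their time on drug. A table that counts a subject once for a flag at any time then mixes a short placebo period with a much longer drug period. A CK, aldolase, troponin I, Hy's Law or QTcF flag that first appears well into open-label treatment would be read as a placebo finding.

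The incidence of potentially clinically significant laboratory and ECG changes is a named secondary endpoint in both documents. If mavodelpar raises the frequency of such values, the excess enters both columns of these tables and the difference between them shrinks.

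**Working it through.** **1. The plan's horizon.** REN001-201 treatment lasts 24 weeks (Protocol 1.4.1: "Phase 2b study to evaluate the efficacy and safety of 24 weeks treatment with REN001"), which is Day 168. REN001-202 Month 48 is Day 1344 (Protocol 6.13; SAP 8.4). With the plan's 28-day months, (168 + 1344)/28 = 1512/28 = 54. The plan's Month 54 is reproduced.

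**2. Share of the placebo column spent on mavodelpar, per subject.**

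- Week 24 rollover completing both studies: 1344/1512 = 88.9% (1344/365.25 = 3.68 years).
- Follow-up rollover, gap assumed at 21 to 35 days (SAP 3.8 expects about 4 weeks): 1344/1533 = 87.7% down to 1344/1547 = 86.9%.
- Interim cut, assuming 6 or 12 study months in REN001-202: 168/336 = 50%, or 336/504 = 67%.
- Placebo subjects who exited first or never enrolled: 0%. Section 2 names only Group 4a for this restriction, but 8.2 applies it to all Exit enrollers.

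**3. Where a late value lands.** Take a Group 1 subject with a first QTcF of PCI at Month 30. The subject is in the REN001-201 safety set. The value is on-treatment under 8.2, because dosing continues and the two studies are treated as one course. Section 12.5 takes the maximum over all such values, and 8.2 puts Group 1 in the placebo column. Nothing in between stops the value. The laboratory PCI rule follows the same path.

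**4. Where a late adverse event lands.** Section 12.1 gives placebo the events reported in REN001-201, so a new REN001-202 event is not placebo's by that rule. Section 8.2, however, limits the REN001 100 mg column to Groups 2, 3 and 4a. Three programming choices remain for the overall table: leave the event under placebo, move it to REN001 100 mg, or omit it. The SAP does not choose.

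**5. Illustrations.** The documents give no event rates, so every rate here is assumed, with constant risk and no dropout.

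- *No drug effect.* With risk p per 24 weeks on either treatment, the risk by Day 1512 is 1 − (1 − p)^9. For p = 1%, 5% and 10% the placebo column shows 8.6%, 37.0% and 61.3%, against 1%, 5% and 10% in the placebo period alone.
- *5% per year on placebo, 10% on drug.* At Day 168 (0.46 years): 1 − exp(−0.05 × 0.46) = 2.3% and 1 − exp(−0.10 × 0.46) = 4.5%, ratio 1.98. At Day 1512: placebo column 1 − exp(−(0.05 × 0.46 + 0.10 × 3.68)) = 32.4%, drug column 1 − exp(−0.10 × 4.14) = 33.9%, ratio 1.05. With 6 or 12 study months of open-label follow-up the ratio is about 1.32 or 1.19.

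**6. Cutting only the placebo arm.** On the same rates the table would read 2.3% against 33.9%. With 5% per year in both arms it would read 2.3% against 1 − exp(−0.05 × 4.14) = 18.7%, a spurious eightfold difference. Cut at the same point, the arms read 2.3% and 4.5%, or 2.3% each when there is no effect.

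**The case against.** The best defence is that carrying the randomised arms to Month 54 is deliberate. A delayed-start view has to follow placebo subjects onto drug, and no formal testing is planned. Most safety tables are by visit, so visits after Month 6 stand apart. The from-start-of-REN001-202 presentation already has a Placebo > REN001 100 mg column on REN001-202 data alone. A separate REN001-201 report also exists, although its contents are not in these documents.

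All of this stands, and it narrows the point to a few any-time displays. It does not supply a placebo-period PCI or QTcF count in this SAP. A reader cannot obtain one by subtracting the REN001-202 table, because a subject flagged in both periods appears in both counts and the two presentations use different baselines.

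The treatment-received wording in 7.2 could be said to settle the matter. It could mean the arm taken in REN001-201 or the drug taken at the time of the value. On the second meaning, Group 1's later values need a column that 8.2 does not provide.

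A reader might also infer that the overall adverse-event counts for placebo contain years of open-label events. The SAP does not say so: 12.1 attributes by treatment, and the onset periods break at Day 168. That is the target day for Week 24 rollovers, who start open-label drug the day after a visit with a window of ±7 days; for follow-up rollovers the break comes about 4 weeks before the switch. Nor do the documents support saying that the drug-placebo contrast is lost across the safety report.

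**Conclusion.** The point holds for the laboratory PCI counts and the maximum-QTcF shift table in the from-start-of-REN001-201 presentation. As written, they count under placebo values first seen on mavodelpar, for placebo subjects who roll over at Week 24 or follow-up. The 88.9% share is the upper end: it assumes nominal visit days, Week 24 rollover and completion of both studies. The share for the whole column will be lower by an amount the documents do not allow one to calculate.

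For adverse events the finding is an ambiguity about which column takes Group 1's REN001-202 events in the overall table. By-visit tables are not affected in this way. The risk ratios in the working show the direction of the dilution and are not estimates for this drug. The change should be made before database lock.

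**What to change.** - In this presentation, show the PCI, maximum-QTcF and overall adverse-event summaries separately for the REN001-201 and REN001-202 periods. Cut **both** arms at the first REN001-202 dose, or at the end of REN001-201 participation for subjects who do not roll over.
- Label Group 1's second-period column Placebo > REN001, and state in 12.1 that its REN001-202 events go there.
- If an all-time summary to Month 54 is kept for the delayed-start view, head that column Placebo > REN001 and give rates per subject-year by the treatment actually taken. Section 9.5 summarises mavodelpar exposure only, so placebo subject-years would have to be derived as well.

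The cost is SAP wording and extra table columns, with no new data. The SAP already attributes concomitant medications to a study period in this presentation (9.4) and lists the assigned emergence period of each adverse event (12.1).

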8 STATISTICAL METHODS

A formal Statistical Analysis Plan (SAP) will be finalized prior to locking the study database. The full details of data presentations and analyses will be provided in the SAP. Additional statistical analyses other than those described in this section may be performed if deemed appropriate and included in the SAP. Any deviations from the final SAP will be discussed in the final Clinical Study Report.

As this study is the open-label extension study to STRIDE, the two studies will be reported together. In addition to data being presented from the start of REN001-202, the data will also be presented from the start of STRIDE and from the start of REN001 treatment for mtDNA-PMM subjects. This will allow the assessment of long-term safety and efficacy from the start of dosing in STRIDE for those who received REN001 in STRIDE, as well as from the start of REN001 in this study.

Presentations from the start of REN001-202 will include all mtDNA-PMM subjects who receive at least one dose of REN001 in this study. The presentations will be split by the various options for entering the study, and by the STRIDE treatment group (REN001, Placebo) for those subjects who participated in STRIDE. nDNA-PMM subjects will also be summarized from the start of REN001-202.

Presentations from the start of STRIDE will include all mtDNA-PMM subjects who receive at least one dose of study drug in the STRIDE study. These will be split by the STRIDE treatment groups (REN001, Placebo). For those subjects who are enrolled into this study after exiting STRIDE only the data collected in STRIDE will be summarized in these presentations.

Presentations from the start of REN001 treatment will summarize the data emergent during treatment with REN001. These summaries will include all mtDNA-PMM subjects who receive REN001 in STRIDE and/or this study.

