8.2.3 Data Summaries

Continuous data will be summarized using descriptive statistics (e.g., mean and standard deviation) and categorical data will be summarized using frequency tables (counts and percentages).

For both safety and efficacy analyses, data used as a baseline measurement will be dependent on the approach to summarizing the data:

- For presentations from the start of REN001-202, baseline will be taken as the last measurement prior to dosing in this study.
- For presentations from the start of STRIDE, baseline will be taken as the last measurement prior to dosing in STRIDE.
- For presentations from the start of REN001 treatment, baseline will be taken as the last measurement prior to REN001 dosing. This will be prior to REN001 dosing in this study for all subjects except those who receive REN001 in STRIDE, where it will be the last measurement prior to dosing in STRIDE.

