3.8. APPROACH TO COMBINING REN001-201 DATA

For mtDNA-PMM subjects, the data from REN001-202 will be combined with data from its feeder study, REN001-201. The combined data will be presented from the start of REN001-201 and from the start of REN001 treatment. Presentations from the start of REN001-201 will include all mtDNA-PMM subjects who receive at least one dose of

study drug in REN001-201 and will continue to acknowledge the randomization to treatment groups at the start of REN001-201.

Presentations from the start of REN001 treatment will summarize the data emergent during treatment with mavodelpar. These summaries will include all mtDNA-PMM subjects who receive mavodelpar in REN001-201 and/or REN001-202. In addition to these summaries, data from REN001-202 alone will be reported which will include mtDNA-PMM and nDNA-PMM subjects. These datasets will provide long-term safety, as well as descriptive information on efficacy measures.

As described in [Section 3.3](#) there are 4 pathway options in which subjects can enter REN001-202. The pathway options are described in more detail below:

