7.2. SAFETY ANALYSIS SETS

There will be a separate safety set for each of the approaches for summarizing the data.

- from the start of REN001-202 – will include all REN001-202 subjects who signed the REN001-202 informed consent form, completed screening and received at least one dose of mavodelpar study medication in REN001-202.
- From the start of REN001-201 – will include all subjects who signed the REN001-201 informed consent form, completed screening and received at least one dose of study medication in REN001-201.
- from the start of REN001 treatment – will include all subjects who signed the informed consent form (REN001-201 form for mavodelpar REN001-201 subjects and REN001-202 form for REN001-201 placebo subjects), completed screening and received at least one dose of mavodelpar study medication in either REN001-201 (mavodelpar subjects in REN001-201) or REN001-202 (placebo subjects in REN001-201).

The ‘from the start of REN001-201’ safety analysis set summaries will be based on the actual treatment received. The safety analysis sets will be used for all baseline and safety analyses.

A listing safety analysis set will be used for listings. This will include all subjects who signed the informed consent form and received at least one dose of study medication in either REN001-201 or REN001-202.

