8.6. BASELINE DEFINITION

Subjects will have up to 2 baselines for endpoints:

- The last available non-missing assessment prior to study drug administration in REN001-201 (Day 1). This baseline will be used for analyses from the start of REN001-201 and, for those who receive mavodelpar in REN001-201, from the start of REN001 treatment analyses.
- The last available non-missing assessment prior to study drug administration in REN001-202. This baseline will be used for analyses from the start of REN001-202, and from the start of REN001 treatment for those subjects who:
 - received placebo in REN001-201
 - enter REN001-202 having exited REN001-201
 - enter REN001-202 having exited REN001-101
 - have nDNA-PMM

For those subjects who enter REN001-202 from REN001-201 at the REN001-201 W24 or FU visits the baseline should be from the assessments at those visits.

Questionnaires collected on the first day of dosing in either study will be considered as a baseline assessment within the context of the above definitions.

Note, to allow for scheduling of the eye examinations and DXA scans the REN001-201 Week 24 (Month 6) assessment can occur up to 14 days or 28 days respectively, after the visit. Hence, this assessment could occur after the start of administration of mavodelpar in REN001-202; this period is not considered sufficient time to have an impact on the results. Therefore, these assessments can still be considered a baseline record provided it occurs within 14 days for eye examinations or 28 days for DXA scans, of the first dose of mavodelpar.

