13. INTERIM ANALYSES

An interim synoptic CSR will be prepared for this study to be included in the regulatory submission package. The data cut will be the date of the last subject last visit in REN001-201 and the data will be extracted from the database after REN001-201 database has been locked. This CSR will include all REN001-202 data up to the data cut date and best efforts will be made to clean data up to this data cut date.

There will be a reduced set of safety outputs generated after submission for the 120-day safety update which is required as part of the submission package. The final CSR will occur after all subjects have had the ability to complete REN001-202, the data has been cleaned and the database locked.

An independently chaired Safety Review Committee (SRC) will review safety data at specified intervals for the duration of the study. The structure, function and operation of the SRC is detailed in the REN001-202 SRC charter. The SRC review of safety data will be limited to data from REN001-202 and will not be combined with REN001-201 data.

**14. CHANGES FROM PLANNED ANALYSES SPECIFIED
IN THE PROTOCOL**

None.

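### The safety set from the start of mavodelpar treatment omits REN001-101 subjects, and counting Group 4a people twice makes its overall AE percentages per treatment course, not per person

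*SAP*

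**What the plan says.** SAP 2 and 8.2 set up three presentations. The one from the start of REN001 treatment covers Groups 1 to 4 in a single pooled REN001 100 mg column, and SAP 2 singles it out for overall AE incidence on mavodelpar. In SAP 8.2, Group 4a is people given mavodelpar in REN001-201 who left and later enrolled in REN001-202; Group 4b is people from REN001-101.

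- **Who belongs.** SAP 3.8: "These summaries will include all mtDNA-PMM subjects who receive mavodelpar in REN001-201 and/or REN001-202". Protocol 8: "These summaries will include all mtDNA-PMM subjects who receive REN001 in STRIDE and/or this study". SAP 8.6 assigns a baseline for this presentation to subjects who "enter REN001-202 having exited REN001-101".
- **Safety set.** The third bullet of SAP 7.2 limits consent to the "REN001-201 form for mavodelpar REN001-201 subjects and REN001-202 form for REN001-201 placebo subjects". Its dosing condition names the same two categories and no other.
- **Counting.** SAP 8.2: "Subjects who enrol in REN001-202 at REN001-201 Exit and receive mavodelpar in REN001-201 [Group 4a] will be counted as 2 separate subjects". SAP 3.8, item 3(a), gives the reason: a gap of variable length, off drug and unmonitored.
- **Tables.** SAP 12 runs the safety evaluations on each safety set. SAP 12.1 reports the number and percentage of subjects, each counted once per SOC or SOC/PT.
- **Baseline.** The first bullet of SAP 8.6 keeps the pre-REN001-201 baseline for those given mavodelpar in that study. The second gives the REN001-202 baseline to those who "enter REN001-202 having exited REN001-201". Protocol 8.2.3 says of the baseline for this presentation: "This will be prior to REN001 dosing in this study for all subjects except those who receive REN001 in STRIDE"; for that exception it is the last value before STRIDE dosing.
- **Change log.** SAP 14, whose heading begins "CHANGES FROM PLANNED ANALYSES SPECIFIED", records none.

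**The concern.** Long-term safety is the primary objective, and this is the presentation meant to show AE incidence on mavodelpar across all mtDNA-PMM subjects. A programmer who follows SAP 7.2 literally has no route by which a REN001-101 subject enters it, although five other sections place that subject there. SAP 9.1 uses subjects dosed with mavodelpar as the denominator for set size, so these people would show as dosed but outside the set.

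The counting rule works in the other direction. Someone with the same preferred term in both courses adds two to the numerator, and every 4a person adds two to the denominator. A reader who takes the column as a share of people would misread it. SAP 7.2 does not describe the second 4a record either, since it admits these people only through REN001-201 consent and dosing.

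**Working it through.** **Step 1: membership.** Group 4b set against each text.

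| Text | REN001-101 subjects dosed in REN001-202 |
|---|---|
| SAP 2 and 8.2 (Groups 1 to 4) | in |
| SAP 3.8 | in |
| SAP 8.6 (baseline assigned) | in |
| Protocol 8 | in |
| SAP 7.2, third bullet | out: neither REN001-201 mavodelpar nor REN001-201 placebo |

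SAP 3.8, item 3(b), restricts these subjects to data from the start of REN001-202. That limits which data are used, not whether the subjects belong.

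**Step 2: baseline, by type of subject who exited REN001-201.**

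| Record | SAP 8.6 | Protocol 8.2.3 | Agree? |
|---|---|---|---|
| 4a, first record | before REN001-201 | before STRIDE (REN001-201) | yes |
| 4a, second record | before REN001-202 | before STRIDE | no |
| Placebo in REN001-201, then Exit | before REN001-202 | before REN001-202 | yes |

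**Step 3: effect of the double count.** The plan states no figure to reproduce. Let n be people in the set, k those in 4a, x people with the event, and m the 4a people with it in both courses.

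- Per person: x/n. Reported: (x + m)/(n + k).
- The reported value exceeds the per-person value only if m/k > x/n.

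Assumptions: n = 150, borrowed from the expected mtDNA-PMM enrolment in SAP 3.5, and 20% per-person incidence (x = 30). The value of k is not in the documents.

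| Case | Lowest (m = 0) | Highest |
|---|---|---|
| k = 10, equal incidence (2 of 10 affected) | 30/160 = 18.75% | 32/160 = 20.0% |
| k = 5, equal incidence (1 of 5) | 30/155 = 19.4% | 31/155 = 20.0% |
| k = 10, 4a incidence 40% (4 of 10; rest 26/140 = 18.6%) | 30/160 = 18.75% | 34/160 = 21.25% |
| k = 10, all 10 affected (rest 20/140 = 14.3%) | 30/160 = 18.75% | 40/160 = 25.0% |

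For a rare term, one 4a person with it in both courses moves the figure from 1/150 = 0.67% to 2/160 = 1.25% at k = 10.

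**Step 4: effect of the omission.** With 1, 5 or 10 people in 4b, the set loses 1/150 = 0.7%, 5/150 = 3.3% or 10/150 = 6.7% of its members, together with any events they had.

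**Step 5: both together.** With b people in 4b, the SAP 7.2 set under SAP 8.2 counting has n − b + k records. At b = k = 10 this is 150 − 10 + 10 = 150. The total looks right, but ten people are missing and ten are there twice.

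**The case against.** The double count is disclosed, stated in two places and reasoned. Protocol 8.1.3 leaves the details of the analysis sets to the SAP, and incidence per treatment start is a legitimate quantity. No hypothesis is tested, the primary endpoints are worded as numbers of events, and the total number of TEAEs is the same either way. All of this stands, so the rule is a choice and not a hidden error. It does not settle the matter, because a gap in dosing justifies two time axes and two baselines but does not turn one person into two in an overall percentage of subjects.

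Four stronger readings are tempting, and the documents do not support them.

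- **REN001-101 safety data are lost.** They are not. These subjects remain in the REN001-202 safety set and in the listing set of SAP 7.2; the loss is confined to the pooled start-of-REN001 tables.
- **The double count inflates AE incidence.** At equal incidence it never raises the figure. It does so only when the share of 4a people affected in both courses exceeds the overall incidence.
- **Every subject who exited REN001-201 has a baseline contrary to the protocol.** Step 2 shows that only the second 4a record does.
- **150 is the size of this set.** It is expected REN001-202 enrolment. The set also holds REN001-201 mavodelpar subjects who never enter REN001-202, a number not given, so the percentages are illustrations.

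**Conclusion.** The third bullet of SAP 7.2 is wrong as written: it contradicts the SAP's own intent and the protocol, and SAP 12 makes it govern the pooled safety tables. It may be a drafting slip, but it needs correcting.

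The 4a rule is a deliberate convention that makes the overall number and percentage of subjects a per-course figure where SAP 2 promises overall incidence. The other two presentations count each 4a person once. The baseline departure is real but limited to one record per 4a person; if the two-record rule is accepted, it follows naturally and needs only to be recorded.

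The numerical effect is probably small, since most transfers are expected at REN001-201 Week 24. Under the illustrative assumptions the double count lowers a 20% incidence by at most 1.25 points when 4a people have the same incidence as the rest (20.0% to 18.75%). Larger movements need 4a people to differ markedly or the event to be rare.

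**What to change.** 1. Add to the third bullet of SAP 7.2 the REN001-101 subjects who sign the REN001-202 consent form and receive at least one dose of mavodelpar in REN001-202.
2. In this presentation, count each 4a person once, in numerator and denominator, in every overall count of subjects that does not depend on a course's own baseline. This covers:
   - the AE overview and SOC/PT tables;
   - demography, medical history, and prior and concomitant medication;
   - set size, and major deviations and COVID-19 where shown for this set;
   - the Troponin I and Potential Hy's Law counts in SAP 12.2, whose criteria have no baseline term.

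   An AE in either course counts once, at its highest severity.
3. Keep two records only for by-visit and by-period summaries, exposure, and baseline-dependent results (the CK and aldolase criteria and the QTcF shift). Footnote the number of 4a people who contribute two records, so that the differing denominators are explained.
4. Record in SAP 14 that the second 4a record uses the REN001-202 baseline, a departure from Protocol 8.2.3.

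The cost is SAP wording, one person-level flag and footnotes. No new data are needed: under SAP 3.6 the REN001-201 subject ID carries over, and the original ID is recorded for anyone rescreened, so the two records can be linked.
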